Therefore, it is important to identify fragile patients to implement prevention programs through global geriatric assessments (CGA Comprehensive Geriatric Assessment). Just by having more clinical attention for more fragile patients after major surgery there can be better results of short and long-term postoperative mortality (22). Likewise, as demonstrated in randomized clinical studies, prehabilitation and global geriatric assessment programs improve the results in terms of postoperative complications and hospital stay (30, 31, 32).

The CGA is an established method to evaluate and optimize the physical state, the psychological, functional and social problems in elderly patients in order to improve the results of the treatments. It implies an interdisciplinary evaluation of multiple domains, followed by planning for analysis, treatment, rehabilitation and long-term follow-up (33).

This allows, in the first place, to intervene before an operation, to increase the physiological reserve of a patient, especially with exercise and nutrition (34, 35). In addition, the therapeutic decision can be guided by adapting the surgical recommendations to the physiological capacity of the patient; second, the knowledge of the increased risk of complications and the possible need for transfer to institutions (especially in patients who live alone) prepares patients and their families for postoperative evolution (8).

The majority of studies published in the literature on the relationship between frailty and postoperative results are retrospective studies, which evaluate populations of patients undergoing major surgery and who, in general, analyze short-term results (30-day mortality) (12, 20, 22, 24, 25, 26, 27, 28, 29). None of these takes into account the impact of surgery on the quality of life of this group of patients. Among all these studies there is very little information about the influence of frailty in gastric cancer surgery. There is only one retrospective study that focuses only on gastric cancer surgery, using the Groningen index and revealing an increase in in-hospital mortality and serious complications (Clavien-Dindo complications score ≥ 3) in fragile patients (25). Objective

The aim of the present study is to assess the impact of frailty on the results of gastric cancer surgery (long-term postoperative morbidity and mortality, hospital stay, readmissions, need of transfer to institution of medium or long stay and quality of life).

Methods

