The characteristics of fragile and non-fragile patient groups will be compared through frequency tables. The Chi-square test will be used to compare the differences between the categorical variables and the ANOVA test for the continuous variables. Different analyzes are proposed according to the study variables that are to be analyzed. For dichotomous type response variables (90- day mortality, 12-month mortality, incidence of serious complications, incidence of in-hospital death in patients with complications, and hospital readmission at 30 days after discharge), a multivariate logistic regression will be used to evaluate the risk (odds ratio) of these variables. For continuous response variables (ICC score) at 30 days after the intervention, and number of days of hospital stay), linear regression models will be used. For the variable categorical response of the patient after hospital discharge, an ordinal logistic regression model will be done. All regression models will be adjusted for age, sex, body mass index (BMI), type of gastrectomy, center volume, neoadjuvant treatment and degree of frailty. Regarding HRQoL analysis, the mean scores and 95% confidence intervals for the different domains of preoperative HRQoL and one year after surgery will be calculated. Changes of more than 10 points on a scale from 0 to 100 will be considered clinically relevant as previously suggested in other publications (40). Work plan The study period includes: Patient recruitment. Follow-up for 1 year to meet the objectives of the study.

The study starts by assessing the fragility of the patients. Once the stage study is completed, the potential curative surgery is determined and after the case presentation in the Multidisciplinary Tumor Committee of each institution, the G8 questionnaires and modified fragility index will be carried out to identify the state and degree of fragility, 2 weeks prior to surgery. The result of the evaluation of the frailty of the patient, will be performed after the Multidisciplinary Committee, thus it will not modify the therapeutic decision.

To measure the Health Related Quality of Life (HRQoL), the QLQ-C30 and QLQ-STO22 questionnaires, will be delivered at the time of the preoperative visit and 12 months after surgery.

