Patients will be asked to fill them in their home. If any patient reports difficulty in understanding the questionnaires, additional help will be provided. Once the questionnaires are received, it will be verified that all the questions have been answered. Otherwise, patients will be contacted in order to complete the questionnaire via telephone. If it is not possible to complete the answers of more than half of the questions on a scale, they will be excluded from the statistical analysis, according to the recommendations of the EORTC (39). All responses from the EORTC QLQ-C30 and STO22 questionnaires will be transformed linearly into scores ranging from 0 to 100 to standardize the score. In functional scales, high scores represent better quality of life (better function) while high scores in symptom scales and items involve more symptoms.

In addition, the variables described in the methodology section will be collected and analyzed:

- Incidence of serious complications (Clavien-Dindo complications score ≥ 3)
- Complication Comprehensive Index (CCI) score during the hospital stay and at 30 days after the intervention
- Incidence of in-hospital death in patients suffering from a complication (failure-to-rescue)
- Hospital stay
- Destination of the patient after hospital discharge
- Hospital readmission within the first 30 days after the discharge
- Mortality at 90 days after the intervention
- Mortality at 12 months after the intervention

In addition to the previously described questionnaires and the main and secondary variables, data related to the prevalence of comorbidities of the patients (Charlson Comorbidity Index, ASA), the stage

study, preoperative optimization, surgical intervention, histopathology and follow-up will be collected. All these data are already systematically collected in the EURECCA Register. Ethical considerations This project is included in the EURECCA Registry, which was presented and approved by the Parc de Salut MAR Clinical Research Ethical Committee (CEIC PSMar) in 2013 in its initial version (nº 2013/5047/I). The amendment of the version, dated 9th June 2016, was approved by the CEIC PSMar and by the respective Clinical Research Ethical Committees of the participating centers. The EURECCA Registry also has a specific Patient Information Sheet and Informed Consent, approved in the 1.2 version of March 2018.

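### The quality-of-life means before surgery and at one year can cover different patients, because the plan sets no paired analysis and no handling of death or unreturned forms

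*Combined protocol and SAP*

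**What the plan says.** HRQoL is part of the study's aim. The Objective section ends its list of outcomes with "need of transfer to institution of medium or long stay and quality of life".

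Under Work plan, the QLQ-C30 and QLQ-STO22 "will be delivered at the time of the preoperative visit and 12 months after surgery". No other assessment is planned.

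The HRQoL analysis takes two sentences in the Statistical analysis plan: "the mean scores and 95% confidence intervals for the different domains of preoperative HRQoL and one year after surgery will be calculated", and "Changes of more than 10 points on a scale from 0 to 100 will be considered clinically relevant". Neither sentence names an analysis set, a within-patient change or a breakdown by frailty.

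The missing-data provisions are in the Work plan text on the questionnaires. Missing answers are chased by telephone, but this starts from a returned form: "Once the questionnaires are received, it will be verified that all the questions have been answered". Then comes a scoring rule: "If it is not possible to complete the answers of more than half of the questions on a scale, they will be excluded". Both deal with gaps in a form that came back. Neither deals with a patient who has died or a form that was never returned.

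The same section lists "Mortality at 12 months after the intervention" as an outcome of its own, and nothing links it to HRQoL.

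**The concern.** The preoperative mean can include everyone who answered before surgery. The 12-month mean can include only patients who are alive and answer then. If the patients who drop out between the two were worse at baseline, the difference between the means mixes real change with a change in who is being averaged.

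The mixing favours a good result: function looks better preserved and symptoms look milder than they were in the patients followed. It is also likely to be stronger in frail patients, because the plan's own sample-size assumption gives them higher early mortality, and the Introduction links frailty to both short- and long-term mortality. At stake is whether a decline beyond the plan's 10-point threshold could be reported as falling short of it.

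**Working it through.** The plan states no HRQoL figure to reproduce, so the check is of the estimator itself.

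**Inputs from the documents (Sample size section).** Assumed 90-day mortality is 4.3% frail and 0.6% non-frail; group sizes are 92 frail and 276 non-frail.

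**Inputs assumed.** The documents give neither the share of patients without a 12-month score (f) nor the baseline gap between retained and lost patients (D). Ranges are used for both.

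**Formula.** Let R be the baseline mean of patients retained to 12 months, L that of patients lost, and D = R − L.

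- Baseline mean of everyone = (1 − f)R + fL
- If no patient changes, the 12-month mean is R, and the apparent change is R − [(1 − f)R + fL] = f × D
- In general, difference of the two means = true change in responders + f × D

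On function scales, worse patients score lower, so D is positive and the mean shifts up. On symptom scales, high scores mean more symptoms, so the sign reverses and the mean shifts down. With change computed within patients who have both scores, f × D drops out by construction.

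**90-day deaths alone, D = 15 (assumed).**

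- Frail: 0.043 × 15 = 0.65 points
- Non-frail: 0.006 × 15 = 0.09 points
- Expected deaths: 92 × 0.043 = 4.0 frail and 276 × 0.006 = 1.7 non-frail

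Loss by 12 months will be at least this, since it adds later deaths and non-response.

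**Total 12-month loss (assumed), shift in points:**

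| Share lost | D = 10 | D = 15 | D = 20 |
|---|---|---|---|
| 10% | 1.0 | 1.5 | 2.0 |
| 20% | 2.0 | 3.0 | 4.0 |
| 30% | 3.0 | 4.5 | 6.0 |
| 40% | 4.0 | 6.0 | 8.0 |

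**Illustration.** Suppose 25% of frail and 10% of non-frail patients are lost and D = 15 in both groups.

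- Frail shift: 0.25 × 15 = 3.75
- Non-frail shift: 0.10 × 15 = 1.5
- Difference between groups: 2.25
- A true 12-point decline in frail responders would read as 12 − 3.75 = 8.25, under the threshold. The 12 is chosen to lie near the threshold.
- Patients lost: 92 × 0.25 = 23 frail and 276 × 0.10 = about 28 non-frail

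**Limit.** With no true change, a shift of 10 points needs D = 10/f: 50 points at 20% loss, 33 at 30%, 25 at 40%.

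**The case against.** The best defence is that the plan is silent rather than wrong. It nowhere says that the first mean covers all patients and the second only responding survivors, and its reference to changes can be read as within-patient change. On that reading the shift is zero. This stands as a caution: the point is that the plan leaves the estimator open, not that it prescribes a biased one. The silence still needs filling, because the only summaries named are two separate means, and even paired change leaves death and unreturned forms unaddressed.

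Deaths are also not hidden, since 12-month mortality is a prespecified outcome with its own adjusted model. That is true, but a reader of the HRQoL result would not see from it how many patients had left each group.

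A reader might infer more than the documents support:

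- *That the patients lost would be mainly frail.* This fits the few assumed 90-day deaths (4.0 against 1.7). It need not hold for total loss: in the illustration more non-frail than frail patients are lost. What is likely to be higher in frail patients is the proportion.
- *That frail patients would look as well as non-frail ones.* The between-group shift in the illustration is 2.25 points, which could hide only a true difference of about that size. The HRQoL sentences also specify no comparison by frailty.
- *That loss would create a clinically relevant improvement.* With no true change, no cell of the table reaches 10 points.

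**Conclusion.** The concern holds as a gap in specification. Followed as written, the plan permits a comparison of means over different patients, and it says nothing about death or unreturned forms in the HRQoL analysis. The direction of the error depends on those lost having had worse baseline scores, which is plausible but not shown in the documents. Its size cannot be derived from them. The 90-day assumptions alone make it negligible, at about 0.65 points (frail) and 0.09 (non-frail) for a 15-point gap. Assumed 12-month loss of 10% to 40% with gaps of 10 to 20 points makes it about 1 to 8 points, which matters for a true decline not far beyond the 10-point threshold. HRQoL is a secondary outcome, but it is in the stated aim and the remedy is cheap, so the plan should be changed.

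**What to change.** Amend the HRQoL paragraph of the Statistical analysis plan:

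1. Make the estimate the within-patient change among patients with both questionnaires, by frailty group, with its 95% confidence interval, and apply the 10-point rule to that change.
2. Beside it, by frailty group, give the number who died before 12 months, the number alive who did not respond, and the baseline means of completers and non-completers.
3. Label the result as applying to 12-month survivors who responded.

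Optionally, add a table that keeps everyone with a baseline score: died / worse by more than 10 / within 10 / better by more than 10 / alive but missing.

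**Cost.** SAP wording and a few tables. Vital status at 12 months is already collected, and no visit is added. The analysis set is smaller, and the estimate speaks only for responding survivors. Precision may go either way. Take 92 baseline scores, 69 pairs (25% lost) and equal variances σ². Two means treated as independent have variance σ²(1/92 + 1/69), and paired change has 2σ²(1 − ρ)/69. The paired interval is narrower once the within-patient correlation ρ exceeds about 0.125.

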Health-Related Quality of Life (HRQoL) will be evaluated with the validated Quality of Life questionnaires of the European Organization for Research and Treatment of Cancer (EORTC-QLQ), QLQ-C30 (30 items Core Quality of Life Questionnaire, version 3.0) and with the specific module for gastric cancer QLQ-STO22 (22 items Stomach Quality of Life Questionnaire).

- The EORTC-QLQ-C30 is a questionnaire that reflects the multidimensionality of HRQoL in patients with cancer. It is composed of 30 questions distributed in five functional scales (physical, role, cognitive, emotional and social), three scales of symptoms (fatigue, pain and nausea and vomiting), a global health scale and a series of additional questions to evaluate symptoms commonly referred by patients diagnosed with cancer (dyspnea, loss of appetite, insomnia, constipation and diarrhea) and the perceived financial impact.
- The EORTC-QLQ-STO22 questionnaire contains 22 structured items in five domains (dysphagia, food restrictions, pain, reflux and anxiety) and four specific items (dry mouth, alteration of taste perception, body image and hair loss) related to the symptoms of the disease.

Sample size

The calculation of the sample size is based on the primary objective of comparing fragile versus nonfragile patients with respect to postoperative mortality at 90 days after the intervention. Based on mortality data previously published in a retrospective study by Mosquera et al. (24), it is estimated that mortality for the group of non-frail patients is 0.6% and for the group with frailty 4.3%. From the data of the literature, a prevalence of 23% of frailty is calculated in the population of patients with gastric cancer and age \geq 70 years undergoing gastrectomy (24). For a power of 80% and a level of significance of 95% in a unilateral analysis, it is estimated that 276 non-fragile patients and 92 fragile patients would be needed to detect as statistically significant the difference between the proportion of patients who die between both groups.

Statistical analysis plan

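### The HRQoL rule concerns change, but intervals are planned only for the separate preoperative and one-year means, so the change carries no measure of uncertainty

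*Combined protocol and SAP*

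**What the plan says.** The HRQoL analysis takes two sentences in the Statistical analysis plan section. The first says that "the mean scores and 95% confidence intervals for the different domains of preoperative HRQoL and one year after surgery will be calculated". The second gives the only criterion for interpretation: "Changes of more than 10 points on a scale from 0 to 100 will be considered clinically relevant".

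HRQoL is not among the outcomes given a regression model. For continuous outcomes the text covers the complication score and "number of days of hospital stay), linear regression models will be used".

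The Objective section lists quality of life among the results on which the impact of frailty is assessed ("need of transfer to institution of medium or long stay and quality of life"). The HRQoL sentences themselves do not mention frailty groups. They also do not say whether the 10-point rule is applied to a group mean or to each patient.

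The only group sizes are in the Sample size section, for 90-day mortality: "276 non-fragile patients and 92 fragile patients would be needed". No precision or power is stated for HRQoL.

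**The concern.** The quantity to be judged (change) and the quantities that get intervals (two means) are different. The uncertainty of a before-after change depends on how strongly each patient's two scores correlate, and on which patients returned both questionnaires. Neither can be recovered from two separate intervals.

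As written, then, a statement that a change did or did not exceed 10 points rests on a point estimate alone. The instruments described under Health-related quality of life yield 24 scales and items. If results are set out by frailty group, one group may cross 10 and the other may not when the true change is the same in both. A reader could take that pattern as an effect of frailty. This would be so even with complete paired data in both groups.

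**Working it through.** **Inputs from the documents.** Threshold: more than 10 points on a 0-100 scale. Group sizes: 92 frail, 276 non-frail. Scales: QLQ-C30 5 + 3 + 1 + 6 = 15, and STO22 5 + 4 = 9, so 24 in all.

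**Assumptions.** The documents give no SD for change. I take 25 points, with a range of 20 to 30, equal in both groups. I first assume no losses at 12 months. The rule is read on group means.

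**The plan's own figure.** There is none for HRQoL. The mortality sample size can be approximately reproduced (0.6% v 4.3%, one-sided 5%, 80% power, 3:1). With pooled proportion (3 × 0.006 + 0.043)/4 = 0.01525, n = (1.645 + 0.842)² × 0.01525 × 0.98475 × 4 / 0.037² ≈ 271.3. That is 272 non-frail and 91 frail, close to 276 and 92. The sizes used below are therefore the plan's own.

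**Step 1. Why two intervals do not give the third.** With equal SD s at both times and correlation r, the standard error of the mean change is s√(2(1 − r)/n). Treating the time points as independent gives s√(2/n). The ratio is 1/√(1 − r): 1.20 at r = 0.3, 1.41 at r = 0.5 and 1.83 at r = 0.7. A reader who combined the two printed intervals would overstate the standard error by 20%, 41% or 83%, and the printed intervals do not reveal r.

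**Step 2. Chance that the observed mean change exceeds 10.** P = 1 − Φ((10 − true)/(SD/√n)). At SD 25 the standard errors are 25/√92 = 2.61 and 25/√276 = 1.50.

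| True change, same in both groups | Frail, n = 92 | Non-frail, n = 276 |
|---|---|---|
| 5 | 2.7% | 0.04% |
| 7 | 12.5% | 2.3% |
| 8 | 22.1% | 9.2% |
| 10 | 50% | 50% |
| 12 | 77.9% | 90.8% |
| 15 | 97.3% | 99.96% |

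Over SD 20 to 30, a true change of 7 gives 7.5% to 16.9% v 0.6% to 4.8%. A true change of 12 gives 83.1% to 73.9% v 95.2% to 86.6%.

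**Step 3. Discordant verdicts with no true difference (SD 25).** At a true change of 7, frail only: 0.125 × 0.977 = 12%; non-frail only: 0.023 × 0.875 = 2%. At 12 the order reverses. Frail only: 0.779 × 0.092 = 7%; non-frail only: 0.908 × 0.221 = 20%.

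**Step 4. Sensitivity to losses.** If 74 frail and 248 non-frail patients remain (assumed losses of about 20% and 10%), a true change of 7 gives 15.1% v 2.9%, and 12 gives 75.4% v 89.6%.

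**Step 5. What the missing intervals would show.** The 95% half-width for mean change is 1.96 × SD/√n. For SD 20 to 30 this is ±4.1 to ±6.1 in 92 patients and ±2.4 to ±3.5 in 276. For the frail minus non-frail difference in change it is 1.96 × SD × √(1/92 + 1/276) = ±4.7 to ±7.1.

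**The case against.** The strongest reply is that HRQoL is a secondary outcome with a descriptive plan, and that 10 points is an interpretive benchmark, not a test. That is fair, and it limits the weight of the point. It does not explain why intervals are given for the two means and not for the change that the benchmark addresses.

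Four stronger readings are tempting, and the documents do not support them.

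- A reader might infer that the plan favours finding relevant change in frail patients. It does not. The excess in the smaller group holds only for true changes below 10. It vanishes at 10 and reverses above. Well below 10 it is small in absolute terms.
- A reader might take it as settled that the frail group is the smaller one. That follows from 92 and 276, but Frailty evaluation names two instruments and does not say which defines the groups. With the stated 23% prevalence and the quoted G8 sensitivity of 92% and specificity of 52%, a score of 14 or less would flag 0.23 × 0.92 + 0.77 × 0.48 = 58% of patients. The non-frail group would then be the smaller and less reliable one.
- A reader might suppose that the sponsor intends to judge change by comparing the two printed intervals. The plan does not say so. Step 1 shows only that those intervals cannot stand in for the missing one.
- A reader might want change called relevant only if its interval lies wholly beyond 10. That would make the label depend on group size. At SD 25 the observed change would have to exceed 15.1 in 92 patients but 12.9 in 276. With a true change of 15 in both groups, a non-frail-only label would arise about 47% of the time (0.914 × 0.517), against about 3% under the present rule.

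The group-mean reading and the frailty split are also inferences. The first is left open; the second comes from the aim. If the rule is meant for individual patients, the probabilities above do not apply. The planned means would still not report it, because no proportion of patients changing by more than 10 is planned.

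**Conclusion.** The concern holds in a limited form. The documents plan no interval, test or model for HRQoL change, although change is what the 10-point rule judges. This needs no assumption.

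The size of the consequence does. On group means, by frailty, with equal SDs of about 25 and the planned 92 and 276, the smaller group's verdict is less reliable in both directions: 12.5% v 2.3% above 10 when the true change is 7, and 78% v 91% when it is 12. The effect matters mainly near the threshold. Which group is affected depends on which is smaller once frailty is defined. The SDs and losses are assumptions, not figures from the documents. The primary mortality analysis is untouched.

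**What to change.** In the HRQoL part of the Statistical analysis plan section:

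1. For each scale, report the mean within-patient change from before surgery to 12 months, with its paired 95% interval, by frailty group.
2. For each scale, report the frail minus non-frail difference in change with its 95% interval. This is the estimate that addresses the aim.
3. State whether the 10-point benchmark is read on group means or on individual patients.
4. Print the interval beside every statement about 10 points.
5. State that one group crossing 10 while the other does not is not evidence of a frailty effect.

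The interval should not be required to lie wholly beyond 10.

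The cost is wording and a little more analysis. Both questionnaires are already planned at both times, under one patient identifier. The downside is that some changes will be shown to be imprecise.
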